3. DESCRIPTION OF DESIGN AND TRIAL POPULATION

3.1 OVERALL TRIAL DESIGN AND PLAN

This will be an open label, multiple dose, multi-centre study to be conducted in around 12-18 centres in 30-40 patients with a diagnosis of moderate to severe active ulcerative colitis, refractory or intolerant to anti-TNF α and/or anti-integrin treatments.

Dose of Neihulizumab will be 9 mg/kg iv. Patients will receive a total of 10 doses on Day 1 (Week 0), Day 8 (Week 1), Day 15 (Week 2), Day 22 (Week 3), Day 29 (Week 4), Day 36 (Week 5), Day 43 (Week 6), Day 50 (Week 7), Day 64 (Week 9) and Day 78 (Week 11). Patients will be followed up on Day 84 (Week 12, End of Treatment, primary endpoint), Day 112 (Week 16), Day 140 (Week 20) and Day 182 (Week 26, End of Study) after the first dose of Neihulizumab.

In some case, patient may be allowed to continue the treatment of study drug in the judgment of the investigator and sponsor medical monitor.

Blood samples for PK determinations will be drawn approximately 15 minutes before dosing and 2 hours post doing at Visits 2, 9 and 11, 15 minutes before doing at Visits 3, 4, 5, 6, 7, 8 and 10, and at Visits 12, 13 and 14. Anti-drug antibodies (ADA) will be determined in all patients before dosing at Visits 2, 6, 10 and at Visits 12-15. Efficacy will be assessed by Mayo Clinic Score (Complete and Partial), endoscopy, biopsy, Inflammatory Bowel Disease Questionnaire (IBDQ) and Biomarkers (faecal calprotectin and c-reactive protein). Safety will be assessed by adverse event (AE) monitoring, laboratory tests, vital signs, physical examinations, discontinuation of treatment due to AE and immunogenicity.

3.2 DISCUSSION OF TRIAL DESIGN

The planned study design including endpoints and methodology is in compliance with regulatory recommendations and consistent with other recently completed phase II studies investigating the efficacy and safety of novel agents in the treatment of UC.

3.3 SELECTION OF TRIAL POPULATION

It is planned that a minimum of 30 and a maximum of 40 patients with moderate to severe UC refractory to anti-TNF α and/or anti-integrin treatments will be entered into this trial. A patient will be considered “enrolled” if they have signed consent and successfully passed the screening phase. Enrollment will be competitive. Approximately 12-18 US sites are planned for this trial.

A log of all patients included into the study (i.e. having given informed consent) will be maintained in the Investigator Site File (ISF) at the investigational site irrespective of whether they have been treated with investigational drug or not.

3.3.1 Main Diagnosis for Study Entry

Moderate to severe active ulcerative colitis refractory or intolerant to anti-TNF α and/or anti-integrin treatments

3.3.2 Inclusion Criteria

1. Patients must provide written informed consent;
2. Aged 18-75 years;
3. Diagnosis of UC \geq 12 weeks prior to screening by full colonoscopy (i.e., \geq 12 weeks after first diagnosis by a physician according to American College of Gastroenterology guidelines);
4. Moderate-to-severe active UC, at time of screening, defined as:
 - a) Mayo Clinic Score (MCS) of 6 points or higher, AND
 - b) a centrally read MCS endoscopic subscore of grade 2 or higher, AND
 - c) MCS rectal bleeding subscore of 1 point or higher, AND
 - d) disease extending 15 cm or more from the anal verge;
5. Stable doses of concomitant medications, including :
 - a) Stable oral corticosteroids (i.e., \leq 20 mg/day of prednisone, \leq 9 mg/day of budesonide) \geq 2 weeks before D1 dosing. Taper of oral corticosteroids per Investigator's discretion during the study is allowed;
 - b) Stable oral 5-aminosalicylic acid dose \geq 2 weeks before D1 dosing;
 - c) Stable immunosuppressant including azathioprine, mercaptopurine, or methotrexate \geq 8 weeks before D1 dosing. Patients taking methotrexate also are advised to take folic acid 1 mg/day or equivalent if there is no contraindication;
 - d) Stable doses of probiotics \geq 2 weeks before D1 dosing;
 - e) Stable anti-diarrheas \geq 2 weeks before D1 dosing;
6. Patients must have previously received anti-tumor necrosis factor alpha (anti-TNF α) and/or anti-integrin therapy for UC and demonstrated an inadequate response, loss of response, or intolerance, and must have discontinued therapy \geq 8 weeks before D1 dosing;
7. Patients previously treated with cyclosporine or tacrolimus must have discontinued therapy \geq 4 weeks before D1 dosing;
8. Topical corticosteroids and topical 5-aminosalicylic acid preparations must have been withdrawn \geq 2 weeks before D1 dosing;
9. Nonsteroidal anti-inflammatory drugs (NSAIDs) must have been discontinued \geq 4 weeks before D1 dosing;

10. Tofacitinib or other Janus kinase (JAK) inhibitors must have been discontinued ≥ 2 weeks before D1 dosing;
11. Patients previously treated with tube feeding, defined formula diets, or parenteral alimentation/nutrition must have discontinued treatment 3 weeks before D1 dosing;
12. Females with reproductive potential must have a negative pregnancy test result before enrollment. Men and women with reproductive potential have to be willing to use a highly effective method of contraception from study start to ≥ 3 months after the final dose of the study drug. A highly effective method of birth control is defined as one which results in a low failure rate (less than 1% per year).

3.3.3 Exclusion Criteria

GI related exclusion criteria:

1. Indeterminate colitis (IBD-U) or suspected Crohn's disease;
2. Any history of colectomy;
3. Presence of an ileostomy or colostomy;
4. A history or evidence of colonic mucosal dysplasia;
5. Short gut syndrome.

General health related exclusion criteria:

6. Pregnant or lactating;
7. Inability to comply with study protocol in the opinion of the investigator;
8. History of dysplasia or malignancy in recent 5 years, except completely excised basal cell carcinoma or squamous cell carcinoma of the skin or carcinoma in situ of the cervix;
9. Cirrhosis or active alcohol abuse per the judgement of investigator;
10. Poorly controlled diabetes (HbA1c $> 8.0\%$);
11. Significant screening ECG abnormalities, including evidence of acute myocardial infarction, complete left bundle branch block, second-degree heart block, or complete heart block;
12. Impaired renal function (calculated creatinine clearance < 60 mL/min);
13. Impaired hepatic function in the absence of diagnosis of primary sclerosing cholangitis serum transaminase $> 2.5x$ ULN, alkaline phosphatase $> 2.5x$ ULN, or increased total bilirubin judged by the investigator to be clinically significant, or a diagnosis of primary

sclerosing cholangitis, serum transaminases > 3x ULN, alkaline phosphatase > 3x ULN, or total bilirubin > 2.5x ULN judged by the investigator to be clinically significant;

14. Moderate to severe anemia (Hb < 8g/dL);
15. Thrombocytopenia (platelet count < 75,000/uL);
16. Evidence of current or previous clinically significant disease, medical condition or finding in the medical examination that in the opinion of the investigator, would compromise the safety of the patient or quality of the data;
17. Requiring parenteral corticosteroid treatment.
18. Received any investigational product within 1 year
19. History of drug abuse according to the Diagnostic and Statistical Manual of Mental Disorders, 5th edition (DSM-V) criteria within 12 months prior to screening or positive drug screening tests.

Infection related exclusion criteria:

20. Human immune deficiency virus (HIV) infection or known HIV-related malignancy;
21. Acute or chronic hepatitis B or C, or carrier status. Patients with anti-HBc Ab but with undetectable anti-HBs Ab should also be excluded;
22. Positive IgM antibody titers in the presence of negative IgG titers to Epstein-Barr virus;
23. Positive stool test for ova or parasites, positive stool culture for pathogens, or positive stool toxin assay for *Clostridium difficile* at screening. Patients with the positive stool toxin assay for *C. difficile* at screening could be rescreened if they are being treated for *C. difficile* and a repeat stool toxin assay at least 4 weeks after the completion of treatment is negative with no evidence of recurrence;
24. Intestinal mucosa biopsy positive for cytomegalovirus (CMV) at screening;
25. Positive screening test for latent *Mycobacterium tuberculosis* (TB) infection. Patients with a history of latent TB infection who received an appropriate and documented course of therapy can be included if the screening examination and a chest x-ray performed ≤ 3 months before screening revealed no evidence of current active infection. If a Quantiferon TB test is indeterminate, the test should be repeated, and if the result is again indeterminate, such patient should be excluded;
26. History of any opportunistic infection ≤ 12 weeks before D1 dosing;
27. Any current or recent (≤ 4 weeks before D1 dosing) symptoms/signs of infection;

28. Received oral antibiotics \leq 4 weeks before D1 dosing or intravenous antibiotics \leq 8 weeks before D1 dosing;
29. Received a live attenuated vaccine \leq 4 weeks before D1 dosing;
30. Neutropenia (absolute neutrophil count $<$ 1,500/uL);
31. Lymphocytopenia (absolute lymphocyte count $<$ 500 /uL);

3.3.4 Patient Withdrawal and Trial Discontinuation

3.3.4.1 Patients withdrawal from the treatment or trial

Patients should make every attempt to complete the protocol as specified. Investigators should encourage compliance with the dosing schedule and completion of all study visits.

It is the right and the duty of the investigator or sub-investigator to interrupt treatment of any patient if they feel that study discontinuation is necessary to protect the patient, or that there are unmanageable factors, that may interfere significantly with the study procedures and/or the interpretation of results. If a patient is withdrawn from study drug, he/she will be encouraged to continue the rest of the visits in [Table 1](#), without receiving study drug.

In accordance with the Declaration of Helsinki, patients have the right to withdraw their consent to participate in the trial at any time, for any reason. In addition, the investigator also has the right to withdraw patients from the study for any legitimate reason.

The patient must be withdrawn from treatment with the study drug in the following cases:

- The patient withdraws consent
- The patient has a worsening in his/her ulcerative colitis (partial Mayo Clinic Score \geq 2 increase compared to baseline)
- The patient is no longer able to participate in the trial for any reason (e.g. surgery, concomitant diseases, concomitant therapies required not allowed by trial or administrative reasons). The patient delays dosing for more than 10 days from the previous dose, or noncompliance while on study
- Patient lost to follow-up
- Investigator's discretion.
- Female participant becomes pregnant

Should a patient decide to withdraw from the study, or should a patient have to be withdrawn from the study, the date (considered End of Study) and the reason for discontinuation shall be recorded on the eCRF, and observation / assessment shall be recorded as thoroughly as possible. All patients withdrawing prior to Day 182 (End of Study) will be asked to allow follow up for

AEs for a minimum of 28 days after the last dose. AEs must be followed until the event has been resolved or no further follow-up is required in the judgment of the investigator and sponsor medical monitor

Patients withdrawn from the trial due to an adverse event must be followed until the event has been resolved or no further follow-up is required in the judgment of the investigator and the trial medical monitor.

The investigator should inform the sponsor immediately when a patient needs to be withdrawn from the trial.

3.3.4.2 Trial discontinuation by the sponsor

AbGenomics reserves the right to discontinue the trial overall or at a particular trial site at any time for the following reasons as long as patients' health/welfare is not compromised:

1. Failure to meet expected enrolment goals overall or at a particular trial site,
2. Emergence of any efficacy/safety information that could significantly affect continuation of the trial.
3. Violation of GCP, Clinical Trial Protocol, or the contract by a trial site or investigator, disturbing the appropriate conduct of the trial.

4. TREATMENTS

4.1 TREATMENTS TO BE ADMINISTERED

The study medication is produced by Boehringer Ingelheim Pharma GmbH & Co. KG.

All doses will be calculated based on mg/kg body weight.

4.1.1 Identity of AbGenomics' Investigational Product

The characteristics of the study medication are listed below

Substance:	AbGn-168H monoclonal antibody (mAb)
Pharmaceutical form:	Infusion concentrate
Chemical name:	Anti-human CD162 (P-selectin glycoprotein ligand-1; PSGL-1) monoclonal antibody (mAb)
Manufacturer:	Boehringer Ingelheim Pharma GmbH & Co. KG
Unit Strength:	Each 2 mL vial contains approximately 1 mL of 40 mg/mL solution
Posology:	Multiple doses
Route of administration:	i.v. (approximately 60 minutes)

4.1.2 Packaging, Labeling, and Re-supply

Drug supplies will be provided by Sponsor's designated CRO. The clinical trial supplies are packaged in a box containing 6 vials. The required information according to the United States Law as well as FDA and other applicable Guideline will be on the boxes and vials.

Each box and vial is labeled with:

- Study number
- Name of product and strengths
- Pharmaceutical dosage form, quantity of dosage units
- Term "for clinical trial use only"
- Sponsor name and address
- Manufacture name and address

- Storage conditions
- Batch number

Label examples are given in the Investigator Site File (ISF).

4.1.3 Storage Conditions

Drug supplies will be kept in their original packaging under the recommended storage conditions, i.e. in a refrigerator with limited access, between + 2°C and + 8°C. A temperature log must be maintained to make certain that the drug supplies are stored at the correct temperature.

The study medication must be stored securely, e.g. at a secure pharmacy. It may only be dispensed to trial patients according to the protocol by authorized personnel as documented in the form “Investigator’s Trial Staff”.

All unused medication must be returned to the sponsor/sponsor designated facility or destroyed on-site per site's standard operation procedure. Receipt, usage and return of study medication must be documented on the respective forms. Account must be given for any discrepancies.

4.1.4 Drug Accountability

The investigator is fully responsible for the investigational products at the trial site. Dispensing of investigational products will be delegated to delegated site staff. The person responsible for dispensing the investigational products will be responsible for maintaining adequate control of the investigational products and for documenting all transaction with them.

The *investigator* and/or *pharmacist* and/or *study medication storage manager* will receive the study medications delivered by the sponsor or sponsor assigned CRO when the following requirements are fulfilled:

- approval of the study protocol by the IRB /ethics committee,
- availability of a signed and dated clinical trial contract between the sponsor or the sponsor assigned CRO and the Trial Centre,
- approval/notification of the regulatory authority, e.g. competent authority,
- availability of the curriculum vitae and medical license of the principal investigator,
- availability of a signed and dated clinical trial protocol or immediately imminent signing of the clinical trial protocol, <in exceptional cases, medication could already be sent to the site, before its activation >

- availability of the Form 1572 and financial disclosure.

Investigational product will be accounted for by the field CRA with the help of delegated site staffs for dispensing the medication. Accountability will be documented by the use of drug accountability forms. The *investigator* and/or *pharmacist* and/or *study medication storage manager* must maintain records (drug accountability forms) of the product's delivery to the trial site, the inventory at the site, the use by each patient, and the return to the sponsor or alternative disposition of unused product(s).

These records will include dates, quantities, batch/serial numbers, expiry ('use by') or retest dates, and the unique code numbers assigned to the investigational product(s) and trial patients. The *investigator/pharmacist/study medication storage manager* will maintain records that document adequately that the patients were provided the doses specified by the clinical trial protocol and reconcile all investigational product(s) received from the sponsor or sponsor assigned CRO.

An inventory must be available for inspection during monitoring visits and will be checked by the field CRA to ensure correct dispensing of the investigational product.

At the time of return to sponsor/sponsor assigned CRO or destruction on-site, the *investigator/pharmacist/study medication storage manager* must verify that all unused or partially used drug supplies have been returned or destroyed and that no remaining supplies are in the investigator's possession.

4.2 TREATMENTS SCHEME, DOSING DELAY AND DISCONTINUATION

A total of 10 doses of Neihulizumab at 9 mg/kg will be administered to patients over 12 weeks on Day 1 (Week 0), Day 8 (Week 1), Day 15 (Week 2), Day 22 (Week 3), Day 29 (Week 4), Day 36 (Week 5), Day 43 (Week 6), Day 50 (Week 7), Day 64 (Week 9), and Day 78 (Week 11). Neihulizumab will be administered intravenously in a total volume of approximately 100 mL over about 1 hour (60 minutes) at a rate of approximately 1.6 to 1.7 mL/min. See [Appendix 10.1](#) for the detailed procedures for preparing Neihulizumab for intravenously administration.

Dosing delay

After the initial infusion, subsequent Neihulizumab infusions can be delayed up to 10 days period due to reversible medical conditions or adverse events or any other reason. If a grade 3 -5 adverse event attributable to the study drug (probably, or definitely related) is observed, additional doses for that patient will be held until the adverse event has returned to baseline. After the adverse reaction is resolved or stabilized, dosing may be restarted if continued

treatment is determined appropriate by the investigator. (unless the adverse reaction is a grade 3 to 5 cytokine release or hypersensitivity reaction, see *Treatment discontinuation* below).

Treatment discontinuation (see also [4.3 Concomitant Therapy and Restrictions](#) and [5.2.2.3 Adverse event and serious adverse event monitoring and reporting](#))

Any patient who experiences a grade 3 to 5 cytokine release or hypersensitivity reaction will be permanently discontinued from Neihulizumab, and withdrawn from the treatment portion of the study. Patients with unambiguous evidence of progression may discontinue Neihulizumab treatment and receive additional therapy per standard institutional guidelines.

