- Severe: Incapacitating or causing inability to work or to perform usual activities, or significantly affects clinical status, and warrants intervention.

Duration of adverse event

The duration of the event will be reported as the start date and stop date of the event.

Causal relationship of adverse event

The relationship between an AE and the use of the investigational product will be determined by a medically qualified Investigator on the basis of his/her clinical judgment, considering all relevant factors, including pattern of reaction, temporal relationship, de-challenge or re-challenge, confounding factors such as concomitant medication, concomitant diseases and relevant history, with the following definitions and causality rating scale (1-3 related; 4-5 not related):

1. Definitely Related: There is evidence of exposure to the test drug. The temporal sequence of the AE onset relative to administration of the test drug is reasonable. The AE is more likely explained by the test drug than by another cause. De-challenge is positive. Re-challenge (if feasible) is positive. The AE shows a pattern consistent with previous knowledge of the test drug or test drug class.
2. Probably related: There is evidence of exposure to the test drug. The temporal sequence of the AE onset relative to administration of the test drug is reasonable. The AE is more likely explained by the test drug than by another cause. De-challenge (if performed) is positive.
3. Possibly related: There is evidence of exposure to the test drug. The temporal sequence of the AE onset relative to administration of the test drug is reasonable. The AE could have been due to another equally likely cause. De-challenge (if performed) is positive.
4. Probably not related: There is evidence of exposure to the test drug. There is another more likely cause of the AE. De-challenge (if performed) is negative or ambiguous. Re-challenge (if performed) is negative or ambiguous.
5. Definitely not related: The patient did not receive the test drug, or temporal sequence of the AE onset relative to administration of the test drug is not reasonable, or there is another obvious cause of the AE.

Assessment of causal relationship should be recorded in the case report forms.

Outcome of adverse event

The outcome of the event will be classified and handled as follows:

Recovered/resolved	The event has stopped. The stop date of the event must be recorded.

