4.2.2.1 Adverse Events

Adverse event (AE) will be coded using the Medical Dictionary for Regulatory Activities (MedDRA) version 20.1. AE will be graded according to CTCAE Version 4.03.

An AE will be considered treatment-emergent (TEAE) if it occurs on or after the first dose of the study medication or it started before the date of the first dose of study medication and worsened after the date of first dose.

Drug-related adverse events are those assessed by investigator as being definitely related, probably related, or possibly related.

Where dates are missing or partially missing, AEs will be assumed to be TEAE, unless there is clear evidence to suggest that AE started prior to the first dose of study treatment. Imputation of partial missing dates will be discussed in section 4.2.1.

Missing relationship to study drug is considered as treatment related in the analyses.

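### Protocol 4.2 gives two incompatible conditions for restarting dosing after a drug-attributed grade 3 or higher event that is stable but not back at baseline

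*Protocol*

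**What the plan says.** Protocol section 4.2, under Dosing delay, sets a mandatory hold for individual patients. The trigger is: "If a grade 3 -5 adverse event attributable to the study drug (probably, or definitely related) is observed". The consequence is that "additional doses for that patient will be held until the adverse event has returned to baseline".

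The next sentence gives the route back to treatment: "After the adverse reaction is resolved or stabilized, dosing may be restarted if continued" treatment is found appropriate by the investigator. It carries one exception, "unless the adverse reaction is a grade 3 to 5 cytokine release or hypersensitivity reaction"; those patients are permanently discontinued from the drug under the Treatment discontinuation paragraph of the same section.

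Three other places bear on the rule:

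- The opening sentence of the same paragraph lets any infusion after the first be delayed by up to 10 days for an adverse event or any other reason.
- Protocol sections 3.3.4.1 and 4.4 require withdrawal when the gap exceeds 10 days, counted from the previous dose.
- The outcome list in Protocol section 5.2.2.1 separates an event that has stopped from one that has settled with lasting residual symptoms.

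**The concern.** A dose-hold rule has to tell the site when the hold ends. Here it gives two end points in consecutive sentences, and they are not the same. An event can stop changing while still worse than the patient's pre-treatment state. For that patient one sentence forbids the next infusion and the other leaves it to the investigator.

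The stake is consistent handling of patients after a severe event attributed to the study drug. A site that re-doses and a site that keeps holding could each point to the text. A monitor could not say which of the two, if either, had deviated from the protocol.

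**Working it through.** No arithmetic is involved in the contradiction itself, so the check sets the sentences side by side.

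**Step 1: which events the rule covers.**

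- Grade: 3 to 5. Restart has no meaning for a grade 5 (fatal) event, so in practice grades 3 and 4.
- Attribution: probably or definitely related.
- Removed by the exception: cytokine release and hypersensitivity reactions of grade 3 to 5.

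**Step 2: apply each sentence to each state the event can be in.**

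| State of the event | Sentence 1 (back to baseline) | Sentence 2 (resolved or stabilized) | Agree? |
|---|---|---|---|
| Gone, patient back at baseline | Hold ends | Restart permitted | Yes |
| Still worsening or fluctuating | Hold continues | Restart not yet permitted | Yes |
| Stable, still above baseline | Hold continues | Restart permitted on investigator judgement | No |

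The conflict is confined to the third row.

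**Step 3: is the third row a real state under this protocol?** Section 4.2 does not define stabilized. The outcome categories in section 5.2.2.1 do, however, recognise an event that has reached a steady state with residual symptoms, and list it separately from a resolved event. So stabilized cannot be read simply as another word for returned to baseline.

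**Step 4: could the two sentences concern different events?** The first speaks of an adverse event and the second of an adverse reaction. That does not separate them, because the trigger is already limited to events attributed to the drug. Nor can the second sentence be meant only for milder events: its exception names grade 3 to 5 reactions, and would be unnecessary if the sentence did not reach those grades.

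**Step 5: how long can the disagreement last?** This depends on the delay limit, which is itself worded in two ways.

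- Counted from the previous dose (sections 3.3.4.1 and 4.4): with a 7-day dosing interval the margin is 10 − 7 = 3 days, so the sentences can diverge on about days 7 to 10 after the last infusion. Beyond that the patient is withdrawn under either sentence.
- Counted as a delay to the next infusion (section 4.2): the window runs to 7 + 10 = 17 days after the last infusion.
- In the later part of the schedule the planned gaps are 64 − 50 = 14 days and 78 − 64 = 14 days. Both exceed 10, so the count from the previous dose cannot be applied there as written.

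The delay limit therefore narrows the period of conflict but does not remove it. It does not say which restart sentence applies within the window.

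**The case against.** The strongest reply is that the second sentence is permissive. Dosing may restart only if the investigator finds it appropriate, and an investigator who keeps holding until baseline complies with both sentences. That is correct, and it means handling is not bound to differ. It does not remove the conflict, because the investigator who re-doses a patient with a stable event complies with one sentence and breaches the other.

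A second reply is that other provisions protect the patient. Any infusion may be delayed for any adverse event, and section 3.3.4.1 gives the investigator both the right and the duty to interrupt treatment. This stands. It limits the possible harm but does not say when a mandatory hold ends.

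A third reply is that the study is over: SAP section 4.1 says it has been closed out. Rewording can no longer change a dosing decision in this trial. The ambiguity still bears on how past holds and restarts are described, and on any later protocol that reuses the text.

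A reader might go further and infer a second contradiction over relatedness. The hold names only probably and definitely related events, while section 5.2.2.1 gives "definitions and causality rating scale (1-3 related; 4-5 not related", with possibly related as rating 3, and SAP section 4.2.2.1 says "Drug-related adverse events are those assessed by investigator as being definitely related, probably related, or possibly related". The documents do not support calling this a contradiction. Section 4.2 states its own threshold for a mandatory hold; the other two places classify events for recording and tabulation. Neither says that every related event must stop dosing, and possibly related events remain open to optional delay and investigator interruption. The narrower threshold may be deliberate, although the protocol does not say so.

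**Conclusion.** Section 4.2 contradicts itself on when dosing may restart. The contradiction covers grade 3 or higher events rated probably or definitely related, other than cytokine release and hypersensitivity reactions, and only while they are stable above baseline.

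Its frequency cannot be determined: the documents give no rate of such events and no record of how sites read the rule. That sites could act differently is an inference from the wording; the documents do not report that it happened.

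Two wider conclusions should be resisted. The first is that every grade 3 or higher event stable above baseline is handled in opposite ways; the exclusions above, the permissive second sentence and the withdrawal limit all rule that out. The second is that the ambiguity measurably raises early discontinuation or lowers the response rate; no figure in the documents supports this.

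The conclusion rests on reading stabilized in its ordinary sense, consistent with the outcome categories in section 5.2.2.1, and on the Amendment 4 text. The wording under which patients were treated in Amendments 1 to 3 is not available here.

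**What to change.** Reconcile the two sentences in Protocol section 4.2 so that one restart condition is stated. If the word stabilized is kept, define it. Which condition applies is for the sponsor and investigators; this review takes no position on it.

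Because the SAP describes the study as closed out, the practical form now is a short statement in the study report of which reading was applied to any patient held under this rule, and corrected text in any later protocol that carries the paragraph forward.

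Separately, and not as a correction, the sponsor may confirm that the relatedness threshold for the hold is intentionally narrower than the definition of related in Protocol section 5.2.2.1 and SAP section 4.2.2.1.

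The cost is a few lines of wording. No planned analysis, sample size or data collection changes.
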